10.2. Analysis of the secondary efficacy criteria

The analysis of the secondary efficacy criteria will involve multivariate analysis.

The selection of variables in multivariate analysis will be performed using a 0.20 significance level and a stepwise method. Covariates considered as potential confounding factors to be initially tested with the treatment in the multivariate models are:

- Body temperature at baseline (°C);
- Scores to each of the items 2 to 7 of the ARSSO at baseline.

All multivariate analyses below will follow this logic.

10.2.1. Modelling of AUC on global score by multivariate ANCOVA

A multivariate ANCOVA model of the AUC on global score of ARSSQ during the first eleven days of the study will be performed.

Patients will be analysed on the FAS and the PP Set.

AXIODIS CRO 17/47

10.2.2. Durations of cold symptoms and of impacts on Quality-of-Life

Hereinafter, the "recovery date" is the first day of the two first consecutive days the patient gave a negative answer to the question 1 ("not sick") without giving a positive answer to the same question (other than "not sick") later. Otherwise, there is no "recovery date" for the patient.

The scores of cold symptoms and of impact on Quality-of-Life (QoL) will be computed at each time-point the patient completed the questionnaire (see §6.4.6), using the following formulae:

At each time point t: ARSSQ_{SYMP}(t) =
$$\sum_{j \text{ in } \{2; ...; 7\}} ARSSQ_{j}(t)$$

ARSSQ_{QOL}(t) = $\sum_{j \text{ in } \{8; ...; 10\}} ARSSQ_{j}(t)$

• The duration of common cold is defined as the duration between the reference start date and the recovery date.

Common cold's duration (days) = Recovery date - Reference start date

The origin date will be the reference start date.

The considered event is the end of common cold, i.e. the recovery of the patient. The event date will be the last day before the recovery date.

Patients without recovery date will be censored at D18 or at the end of the study, and the censoring date will be the date of D18 or the reference end date, whichever occurs first.

• The duration of the cold symptoms is defined as the duration between first symptomatic day and last symptomatic day.

Cold symptom's duration (days) = Last symptomatic day - first symptomatic day + 1

The first symptomatic day is the first day the patient had a non-zero and non-missing score of cold symptoms. It will be the origin date.

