The last symptomatic day is defined as the day before the two first consecutive days the patient had a zero score of cold symptoms without having a non-zero and non-missing score of cold symptoms later. The considered event is the end of cold

AXIODIS CRO 18/47

symptoms, i.e. the definitive nullification of the corresponding score during at least two consecutive days.

The considered symptomatic days are between D1 and either D18, or the end of the study, or the day before the recovery date, whichever occurs first. Symptomatic days from the recovery date will not be taken into account.

For patients who definitely nullified the score of cold symptoms, or for patients with a recovery date, the event date will be the last day before the definitive nullification of the score of cold symptoms, or before the recovery date if it exists.

Patients who did not definitely nullify the score of cold symptoms, and without recovery date, will be censored at D18 or at the end of the study, and the censoring date will be the date of D18 or the reference end date, whichever occurs first.

For patients who never had a non-zero score of cold symptoms (never ticked "mild", "moderate" or "severe" for any symptom) and having completed the questionnaire at D1, the origin date for the symptom will be D1, the cold symptoms will be censored at D1 and the duration will be zero. If patients who never reported the presence of any symptom did not complete the questionnaire at D1, neither origin date nor censoring date will be defined for cold symptoms and the duration will be missing.

• The duration of impact on QoL is defined as the duration between first impacted day and last impacted day.

Impact on QoL's duration (days) = Last impacted day – first impacted day + 1

The first impacted day is the first day the patient had a non-zero and non-missing score of impact on QoL. It will be the origin date.

The considered event is the end of impact on QoL, i.e. the definitive nullification of the corresponding score during at least two consecutive days. The last impacted day is defined as the day before this definitive nullification, and the duration is computed by the same way as for cold symptoms' duration.

A Cox survival regression model will be used to analyse each of the durations of common cold, of cold symptoms and of impact on QoL.

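### SAP 10.2.2 gives two end points for a child whose symptoms or impacts clear before question 1 reads 'not sick': the formula ends at clearance, while the event-date sentence, read literally, ends at the common-cold event date

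*SAP*

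**What the plan says.** SAP 10.2.2 analyses three durations: common cold, cold symptoms (items 2 to 7) and impact on QoL (items 8 to 10).

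- **Common cold.** Duration is the recovery date minus the reference start date. The event falls on the day before the recovery date. The recovery date rests on question 1 alone.
- **Cold symptoms, duration.** It "is defined as the duration between first symptomatic day and last symptomatic day", with the formula "Cold symptom's duration (days) = Last symptomatic day - first symptomatic day + 1". The last symptomatic day is the day before the first two consecutive "days the patient had a zero score of cold symptoms without having a non-zero and non-missing score of cold symptoms later".
- **Cold symptoms, event.** The event is "the definitive nullification of the corresponding score during at least two consecutive days".
- **Cold symptoms, event date.** The sentence applies both to children whose score has cleared for good and to children who have recovered on question 1. It places the event on the day before that clearance and then adds "or before the recovery date if it exists".
- **QoL.** The origin is the first impacted day, and "the duration is computed by the same way as for cold symptoms".

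The sentence on which symptomatic days count and the sentence on censoring both say that the first-occurring limit applies. The event-date sentence between them does not.

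**The concern.** The formula and the defined event look only at the child's items. The event-date sentence brings in question 1 and, taken literally, lets a recovery date replace an earlier clearance of the items. A child whose items clear first therefore has two end dates within one section.

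The rest of the plan gives no reason to extend a duration past clearance. Protocol 7.1.4 ends each duration on the item itself, absent or without impact for two consecutive days, and does not use question 1. SAP section 12 brings in question 1 for the opposite case, in which symptoms are still ticked after the child is no longer sick. That use can only shorten a duration.

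A named secondary objective is at stake, the effect on symptom duration and on quality of life. Under the literal rule, an improvement in symptoms or activities that precedes 'not sick' would not move the symptom or QoL event. There is also a reporting risk. Mock T15 shows descriptive durations and a hazard ratio in one table. If the first come from the formula and the second from the event date, they describe different variables.

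**Working it through.** **The plan's own figures.** The documents state no event count, hazard ratio or power for the duration models. The only powered figure is for the primary AUC: 100 per arm for an effect size of 0.4 at 80% power and 5% two-sided type I error. It reproduces (99 per arm needed; 80.4% power at 100 per arm by the exact t-test) but does not bear on this point.

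**Notation.** F is the first symptomatic (or impacted) day, Z the first day of the definitive zero score and R the recovery day.

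- Formula duration when Z comes first: (Z − 1) − F + 1 = Z − F.
- Time to the literal event date, counted the same way: (R − 1) − F + 1 = R − F.
- Common-cold duration: R − 1, with D1 as reference start.

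The first two differ by R − Z whenever Z < R. When Z > R, the SAP ignores symptomatic days from recovery onward, and both give R − F. With F = 1 the literal time is R − 1, exactly the common-cold duration. F = 1 is the expected origin for symptoms, because Protocol 7.3.1.1 requires at least moderate nasal congestion at entry.

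| Case | Zero from | 'Not sick' from | Formula | Literal event date | Common cold |
|---|---|---|---|---|---|
| Symptoms, F = D1 | D6 | D9 | 5 | 8 | 8 |
| Symptoms, F = D1 | D5 | D8 | 4 | 7 | 7 |
| Symptoms, F = D1 | D4 | D10 | 3 | 9 | 9 |
| Symptoms, F = D1 | D8 | D8 | 7 | 7 | 7 |
| Symptoms, F = D1 | D10 | D8 | 7 (capped) | 7 | 7 |
| QoL, F = D3 | D5 | D8 | 2 | 5 | 7 |

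The conflict arises only where items clear first. In the QoL row the end date matches the common-cold event date (D7), but the length differs by F − 1 = 2 days.

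**Effect on the hazard ratio.** All inputs below are assumptions, with 100 children per arm. A hazard ratio above 1 favours the active spray.

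1. *Effect on items only.* Recovery day has a mean of about 9 in both arms. A share of placebo children clear 1 to 4 days before 'not sick', and the share on active is 1.5 times as large. Placebo shares of 20%, 40% and 60% give formula hazard ratios of 1.07, 1.12 and 1.22. The literal rule gives 1.02, 1.00 and 1.01. Among children with a recovery date, symptom and common-cold times are identical in 100% under the literal rule, against 75%, 50% and 25% under an earlier-of rule.
2. *Varying the lag.* Items clear at a mean of day 5.0 on placebo, and clearing time is 25% shorter on active. The formula gives a hazard ratio of about 1.74 to 1.78, with power of about 95% or more.
   - Mean lag 2.5 days, question 1 shortening in parallel: literal rule 1.46 to 1.48, power 73% to 78%.
   - Mean lag 1 day, in parallel: 1.67, power still about 95%.
   - That 1-day lag in only 40% of children: 1.68.
   - Mean lag 2.5 days, no effect on question 1: 1.00 to 1.02, 'power' 5% to 6%. The null result follows directly from the assumption.

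In the parallel cases it is the spread of the lag that dilutes the effect. A lag identical for every child would leave the order of events, and so the hazard ratio, unchanged apart from censoring at D18.

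**The case against.** The strongest reply is that the literal reading was probably not intended. The event is defined as nullification of the score. The neighbouring sentence treats recovery as an upper limit. Section 12 uses question 1 only to cut off late symptoms. The event-date sentence opens by naming two groups of children, so its two dates can be read as one per group. On that reading the gap is confined to the child who belongs to both. The SAP also says that the Cox model analyses each of the durations, and each duration has a formula. If the formula supplies the time, nothing collapses.

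Much of this stands. An earlier-of rule is the most coherent intention. However, the text does not state it, and a child with both dates is the ordinary case in a self-limiting illness whose diary stops on question 1. The SAP also defines origin, event and censoring dates without saying whether they or the formula supply the analysis time.

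A reader might infer that the three Cox and Kaplan-Meier analyses simply repeat one outcome. The documents do not support that. QoL starts at the first impacted day, and a child without a recovery date can have a symptom event yet be censored for common cold. A reader might also infer a definite loss, for example from at least 95% to 73% power. That rests on an assumed mean lag of 2.5 days. No document gives the lag, and the only disagreement that section 12 reports runs the other way.

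**Conclusion.** The inconsistency is real. For a child whose symptom or QoL score clears before recovery, the formula and the defined event end on the day before clearance. The event-date sentence, read literally, ends on the day before recovery. The discrepancy is R − Z days for that child.

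The consequence is conditional. If the analysis time is taken from the event date, symptom and common-cold durations are equal for every child with a recovery date and a D1 origin. QoL shares the end date, and matches in length only if impact starts on D1. A benefit that precedes 'not sick' is then diluted or hidden. The loss may be slight (about 1.74 to 1.67 on the hazard ratio) or total, depending on the lag and on whether question 1 also responds to treatment. If the analysis time is the formula duration, the models are unaffected and only the wording conflicts.

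The primary AUC is untouched. SAP 6.3.1 treats the secondary results as descriptive, with p-values for information only. The sentence should be corrected, but the trial's main conclusion does not depend on it.

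**What to change.** Replace the event-date sentence in SAP 10.2.2 with: *the event date is the day before definitive nullification of the score or the day before the recovery date, whichever occurs first*. Define the last symptomatic day, and the last impacted day for QoL, in the same way. State that the Cox and Kaplan-Meier time is the resulting formula duration, so that Mock T15 and the curves use one variable.

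With this rule the duration is min(Z, R) − F. The table's cases become 5, 4, 3, 7, 7 and 2 days, in agreement with the formula column.

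Dropping question 1 from the rule altogether would not work. A child who recovers on question 1 but never has two consecutive zero-score days, the case section 12 was written for, would have no event date. The earlier-of wording covers that child.

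The cost is one sentence, one matching definition and a small programming change, with no new data. Record the clarification in SAP section 12.

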7.1.3 Primary Endpoint with methods and timing for assessing recording and analysing variables

The AUC of the global score of the Acute Rhinitis Symptoms Severity Questionnaire (ARSSQ) during first 11 days of symptoms will be compared between both groups.

ARSSQ is a non-validated customized questionnaire (Appendice 1). It includes 10 items assessing symptoms, functional impairments, and global severity. Each item is scored from 0 (not present/no impact/ not sick) to 3 (severe, severe impact and very sick) for symptoms, functional impairment and global severity respectively. Parents/legal guardians will respond to questions according to the evolution of their child's symptoms. This questionnaire is based on the most common symptoms reported for children with common cold and on functional impairments easily evaluable by parents. In order to evaluate the time dependent efficacy of active/placebo, an AUC computation will be carried out.

The ARSSQ assessment will be completed in a paper diary once daily in the evening, taking into account the symptoms from the morning to the evening, within D2-D8 period. After D8, the ARSSQ will be assessed once daily until resolution of all symptoms for 2 consecutive days (question 1 of the questionnaire "not sick" ticked). At D1, the ARSSQ will be completed during the screening/inclusion visit V1. If the patient still has symptoms at V2, ("not sick" not ticked for 2 consecutive days in the previous days), the questionnaire will be also completed during the visit.

To be noticed that the duration may be censored at the end of study participation (visit V2, between day 15 and D18 after inclusion).

- 7.1.4 Secondary Endpoints with methods and timing for assessing, recording and analysing variables
- Comparison of duration of each cold symptom (questions 2 to 7 of the ARSSQ) in both groups.

For each separate symptom, the duration is defined as the number of days between Day 1 and the first day the parent/legal guardian reports the patient not having this symptom ("Not present") for 2 consecutive days.

As mentioned for primary endpoint, duration may be censored at Visit 2.

- Comparison of duration of quality-of-life impairment (questions 8 to 10 of the ARSSQ).

For each separate activity, the duration is defined as the number of days between Day 1 and the first day the parent/legal guardian reports no impact on the patient quality of life ("No impact") for 2 consecutive days.

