7.3.1 Eligibility Criteria

7.3.1.1 Inclusion Criteria

Subjects will be enrolled if they meet all of the following criteria:

- 1. Male/Female subjects >2 and ≤6-year-old
- 2. Acute infectious rhinitis/rhinosinusitis for ≤48h before trial entry
- 3. Patient presenting with fever ≥ 37.5 °C at screening
- 4. Subjects with nasal congestion (blocked / stuffy nose) rated at least as moderate on the Acute Rhinitis Symptoms Severity Questionnaire, based on evaluation by the investigator
- 5. Subjects showing at least moderate grade for at least one of the following additional signs of acute rhinitis: runny nose, nasal crust (dry mucus), sneezing and cough
- 6. Written consent obtained from parent/legal guardians

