2.2. Secondary objectives

The secondary objectives are:

- To assess the impact of **Healsea® Babykids** on the duration of each infectious rhinitis symptom and on quality of life as compared to Placebo;
- To assess the impact of **Healsea**[®] **Babykids** on the intake of conventional common cold medications (antibiotics, antipyretics, mucolytics, decongestants, antitussives, systemic and topical corticosteroids) as compared to Placebo;
- Safety: to assess systemic and local tolerance of **Healsea**® **Babykids** over the study period.

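### The protocol's nine per-item durations (six symptoms, three activities) are not analysed in the SAP, and SAP 12 does not declare that they were pooled and redefined

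*SAP*

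**What the plan says.** Protocol 7.1.4 (and the synopsis) defines the duration endpoints item by item. For symptoms: "For each separate symptom, the duration is defined as the number of days between Day 1 and the first day" of two consecutive days on which the parent reports the symptom absent. For quality of life: "For each separate activity, the duration is defined as the number of days between Day 1 and the first day" of two consecutive days without impact. Both may be censored at Visit 2.

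SAP 2.2 repeats the objective: to assess the impact "on the duration of each infectious rhinitis symptom and on quality of life as compared to Placebo".

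SAP 10.2.2 then defines three durations:

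- a common cold duration, from the inclusion visit to recovery on question 1;
- a cold symptom duration, based on the sum of questions 2 to 7;
- a quality-of-life duration, based on the sum of questions 8 to 10.

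A Cox model "will be used to analyse each of the durations of common cold, of cold symptoms and of impact on QoL". The output list in SAP 13.1 has tables and figures for these three only, and the listing of durations covers the same three.

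SAP 12, which lists changes from the protocol, declares that the primary analysis was replaced. It also declares, with a reason, that question 1 is now used to end the symptom and quality-of-life durations. It does not mention pooling.

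**The concern.** The SAP restates an objective on each symptom but plans no result for any single symptom. Congestion is the clearest loss, because it is the one ARSSQ item that every child must have at entry: "Subjects with nasal congestion (blocked / stuffy nose) rated at least as moderate on the Acute Rhinitis Symptoms Severity Questionnaire" (Protocol 7.3.1.1). The report could not say whether congestion, or any other single symptom or activity, was shortened.

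The record of changes is also incomplete. Someone who relies on SAP 12 would learn of the question 1 end rule but not that nine endpoints became two sum-score durations, or that the start of the clock and other rules changed. SAP 12 still speaks of a single symptom and its absence, which suggests that item-level durations remain when they do not.

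**Working it through.** **The plan's own figure.** The only sized endpoint is the primary AUC: effect size 0.4, 80% power, two-sided 5%, 100 per arm. It reproduces: 2 × (1.960 + 0.842)² / 0.4² = 98.1, so 99 per arm (t-based 99.1, so 100). It has no bearing on the durations, none of which is sized.

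**Count of endpoints.**

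| Source | Durations |
|---|---|
| Protocol 7.1.4 | 6 symptoms + 3 activities = 9, all per item |
| SAP 10.2.2 | 1 on question 1 + 2 on sum scores = 3, none per item |
| SAP 13.1 | 3 Cox tables; 3 × 2 = 6 figures (forest plot, Kaplan-Meier); none per item |

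So 0 of the 9 protocol durations are analysed.

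**Formulas.**

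- Protocol: first of two consecutive clear days − Day 1.
- SAP sum scores: last non-zero day − first non-zero day + 1, with no later non-zero score, and cut off at question 1 recovery.

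The protocol wording is read as a simple difference. Adding one day to each protocol value would not change the contrasts in (a).

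The diaries below are hypothetical. They show how the rules behave and do not estimate an effect. All assume no earlier question 1 recovery.

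**(a) Pooling.** Sneezing/cough is present from D1 to D9 and clear from D10. All other symptoms are clear by then.

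- Congestion first clear at D8: protocol 8 − 1 = 7 days.
- Congestion first clear at D5: protocol 5 − 1 = 4 days.
- SAP symptom duration in both cases: 9 − 1 + 1 = 9 days.

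A three-day difference in congestion leaves no trace in the pooled value.

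**(b) Origin.** The SAP starts the quality-of-life clock later than Day 1: "The first impacted day is the first day the patient had a non-zero and non-missing score of impact on QoL". Suppose one activity is affected and the other two are clear throughout.

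- Clear on D1, affected D2–D5, clear from D6: protocol 6 − 1 = 5 days; SAP 5 − 2 + 1 = 4 days (shorter).
- Clear on D1–D3, affected D4–D7, clear from D8: protocol 1 − 1 = 0 days; SAP 7 − 4 + 1 = 4 days (longer).

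For the symptom sum the effect should be small, because required congestion makes D1 the first non-zero day.

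**(c) Relapse.** A symptom is present D1–D4, absent D5–D6, present D7 and clear from D8. Every other symptom is zero on D5–D6 and from D8. Protocol: 5 − 1 = 4 days. SAP: 7 − 1 + 1 = 7 days.

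**SAP 10.2.2 set against SAP 12.**

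| Change from Protocol 7.1.4 | In SAP 12? |
|---|---|
| Question 1 can end a duration | Declared and explained |
| Items pooled into sum scores | No |
| Origin moved to first non-zero day | No |
| Common cold duration added | No |
| Never-affected children censored at D1 with zero duration | No |
| No later relapse allowed | In part: written for children whose last completion days were not consecutive, and not presented as a change |

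**The case against.** The best defence is Protocol 8.4. It plans Cox models for the duration of symptoms and of quality-of-life impact in grouped words, while the same section asks for a breakdown by drug class for medications. The SAP follows that wording, and it is fair to say that the protocol is not uniform. But section 8 introduces itself as a summary, 7.1.4 holds the definition, and SAP 2.2 still says each symptom.

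A second defence is that SAP 6.3.1 makes every secondary result descriptive. That limits the harm, and it is a good reason not to ask for a full set of outputs per item. It does not excuse the omission: a descriptive endpoint still has to be described, or its removal declared.

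Several stronger readings are tempting, and the documents do not support them.

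- A reader might infer that the whole secondary objective is unanswered. Its quality-of-life part is worded generally, and the pooled quality-of-life duration addresses it. What is lost there is the per-activity endpoint.
- A reader might infer that the relapse condition is hidden. SAP 12 writes part of it.
- A reader might fault the question 1 rule as arbitrary. It is declared, and it builds on the protocol's own use of question 1 to mark resolution.
- SAP 12 explains that rule by what several patients reported, so a reader might suspect that treatment was known. Nothing shows this: Protocol 7.1.2 and 9.3 place unblinding after database lock and a blind review before it.
- A reader might infer a loss of power or a biased treatment effect. No figure in the documents allows either to be estimated.

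**Conclusion.** The point holds. None of the nine durations defined in Protocol 7.1.4 is analysed, so the each-symptom part of a stated objective has no result and the per-activity endpoint disappears. SAP 12 is incomplete on the durations: the pooling, the moved origin, the added common cold duration and the D1 zero-duration censoring are missing, and the relapse condition is only partly there.

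This should be fixed, but it does not threaten the trial. The primary AUC comparison is unaffected, and p-values on secondary criteria carry no inferential weight. The conclusion rests on treating 7.1.4 as the governing definition. The day counts rest on the hypothetical diaries and show only that the rules can differ.

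**What to change.** 1. **Add a compact descriptive analysis of the nine item durations** under the protocol definition: one table with the median and a treatment-only hazard ratio with 95% CI for each item, and one forest plot. Kaplan-Meier graphs are optional. SAP 10.2 says "The selection of variables in multivariate analysis will be performed using a 0.20 significance level and a stepwise method"; a treatment-only model avoids nine different covariate sets and keeps the items comparable. State that a child without the item on D1 and D2 has 0 days under the protocol wording, and how that child enters the model.
2. **Set one censoring rule.** The diary can stop before Visit 2: "After D8, the ARSSQ will be assessed once daily until resolution of all symptoms for 2 consecutive days", judged on question 1 (Protocol 7.1.3). Censor each item at the earlier of the last completed ARSSQ and Visit 2. As a sensitivity analysis, count items still positive when the diary stops as events at question 1 recovery. Note that this censoring may be informative.
3. **Keep the common cold duration and the two sum-score durations** as supplementary.
4. **Complete SAP 12.** Declare and justify the pooling, the moved origin, the no-later-relapse condition, the added common cold duration and the D1 zero-duration censoring. Align its single-symptom wording with 10.2.2.

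Cost: some item-level programming on diary data already collected, one table, one figure and one sensitivity table. Data collection, sample size and the primary analysis do not change. The drawback is more intervals or p-values without inferential weight. Nine independent tests at 0.05 would give 1 − 0.95⁹ = 37% chance of at least one false positive (illustration only, since the items are unlikely to be independent), so the results should stay descriptive.
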